10.14 APPENDIX 14: EQ-5D-5L

28-Oct-2023 Version number: 1

10.15 APPENDIX 15: DEFINITION OF ANAPHYLAXIS

"Anaphylaxis is a serious allergic reaction that is rapid in onset and may cause death (27)."

Clinical criteria for diagnosing anaphylaxis

Anaphylaxis is highly likely when any one of the following 3 criteria are fulfilled:

- Acute onset of an illness (minutes to several hours) with involvement of the skin, mucosal tissue, or both (eg, generalized hives, prunitus or flushing, swollen lips-tongue-uvula)
 - AND AT LEAST ONE OF THE FOLLOWING
 - a. Respiratory compromise (eg, dyspnea, wheeze-bronchospasm, stridor, reduced PEF, hypoxemia)
 - b. Reduced BP or associated symptoms of end-organ dysfunction (eg, hypotonia [collapse], syncope, incontinence)
- 2. Two or more of the following that occur rapidly after exposure to a likely allergen for that patient (minutes to several hours):
 - a. Involvement of the skin-mucosal tissue (eg, generalized hives, itch-flush, swollen lips-tongue-uvula)
 - b. Respiratory compromise (eg, dyspnea, wheeze-bronchospasm, stridor, reduced PEF, hypoxemia)
 - c. Reduced BP or associated symptoms (eg, hypotonia [collapse], syncope, incontinence)
 - d. Persistent gastrointestinal symptoms (eg, crampy abdominal pain, vomiting)
- 3. Reduced BP after exposure to known allergen for that patient (minutes to several hours):
 - a. Infants and children; low systolic BP (age specific) or greater than 30% decrease in systolic BP*
 - b. Adults: systolic BP of less than 90 mm Hg or greater than 30% decrease from that person's baseline

PEF, Peak expiratory flow; BP, blood pressure.

*Low systolic blood pressure for children is defined as less than 70 mm Hg from 1 month to 1 year, less than (70 mm Hg + $[2 \times age]$) from 1 to 10 years, and less than 90 mm Hg from 11 to 17 years.

10.16 APPENDIX 16: LIST OF OPPORTUNISTIC INFECTIONS

- Aspergillosis.
- Blastomyces dermatitidis (endemic in the south-eastern and south-central states US, along Mississippi and Ohio Rivers).
- Candidiasis only systemic or extensive mucosal or cutaneous candidiasis.
- Coccidioides immitis (endemic south-western US and Central and South America).
- Cryptococcus.
- Cytomegalovirus.
- Herpes Simplex (disseminated).
- Herpes Zoster (disseminated; ophthalmic; involvement of 2 or more dermatomes).
- Histoplasmosis (pulmonary or disseminated; most common tropical areas Tennessee-Ohio-Mississippi river basins).
- Listeriosis.
- Mycobacterium tuberculosis.
- Mycobacterium avium.
- Nontuberculosis mycobacteria.
- Pneumocystis pneumonia (PCP).

This list is indicative and not exhaustive.

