7.1.1 Permanent discontinuation

In rare instances, it may be necessary for a patient to permanently discontinue study intervention. If study intervention is permanently discontinued, the participant remains in the study to be evaluated for as per Section 1.3.2 (see the SOA for data to be collected at the time of discontinuation of study intervention).

Permanent intervention discontinuation is any intervention discontinuation associated with the definitive decision from the Investigator not to re-expose the patient to the IMP at any time during the study, or from the patient not to be re-exposed to the IMP whatever the reason.

List of criteria for permanent discontinuation of study intervention

All efforts should be made to document the reason(s) for discontinuation of study intervention and this should be documented in the eCRF.

Patients must be withdrawn from the study intervention for the following reasons:

- At their own request or at the request of their legally authorized representative (legally authorized representative means an individual or judicial or other body authorized under applicable law to consent on behalf of a prospective patient to the patient's participation in the procedure(s) involved in the research).
- If, in the Investigator's opinion, continuation on the study intervention would be detrimental to the patient's well-being.
- At the specific request of the Sponsor.
- In the event of a protocol deviation, at the discretion of the Investigator or the Sponsor.
- Any code broken requested by the Investigator will lead to permanent discontinuation of study intervention.
- Pregnancy.

- Anaphylactic reactions or systemic allergic reactions that are related to IMP and require treatment.
- Diagnosis of a malignancy during study, excluding carcinoma in situ of the cervix, or squamous or basal cell carcinoma of the skin.
- Any opportunistic infection, such as TB or other infections whose nature or course may suggest an immunocompromised status (see Section 10.16, Appendix 16).
- Serum ALT >3 ULN and Total Bilirubin >2ULN (see Section 10.6, Appendix 6).
- Serum ALT >5 ULN if baseline ALT ≤2 ULN or ALT >8 ULN if baseline ALT >2 ULN (see Section 10.6, Appendix 6).
- If the patient misses more than 3 consecutive doses, the patient will be permanently discontinued from the study intervention.

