8.3.1 Adverse event of special interest

An adverse event of special interest (AESI) is an AE (serious or nonserious) of scientific and medical concern specific to the Sponsor's product or program, for which ongoing monitoring and immediate notification by the Investigator to the Sponsor is required. Such events may require further investigation in order to characterize and understand them. Adverse events of special interest may be added, modified or removed during a study by protocol amendment.

For these AESIs, the Sponsor will be informed immediately (ie, within 24 hours), per SAE notification described in Section 8.3.2, even if not fulfilling a seriousness criterion, using the corresponding pages in the CRF (to be sent) or screens in the e-CRF. If an SAE or any AESI of anaphylactic reactions or systemic allergic reactions that are related to IMP and require treatment, or severe injection site reactions lasting longer than 24 hours, occurs in a patient, blood samples should be collected for determination of functional dupilumab concentration, and ADA assessment at or near the onset and completion of the occurrence of the event, if possible (see Section 8.5.3 for details).

- Clinically symptomatic eosinophilia (or eosinophilia associated with clinical symptoms).
- Anaphylactic reactions or systemic allergic reactions that are related to IMP and require treatment (see Appendix 15, Section 10.15).
- Severe injection site reactions that last longer than 24 hours.
- Any infection meeting at least one of the following criteria:
 - Any serious infection (SAE).
 - Requires parenteral (intravenous, intramuscular, subcutaneous) antimicrobial therapy.
 - Requires oral antimicrobial therapy for longer than 2 weeks.
 - Is a parasitic infection.
 - Is an opportunistic infection (see Appendix 16, Section 10.16).

Note: antimicrobial therapy refers to antibiotic, antiviral, and antifungal agents

- Any severe type of conjunctivitis or blepharitis.
- Keratitis.
- Significant ALT elevation:
 - ALT >5 × the upper limit of normal (ULN) in patients with baseline ALT \leq 2 × ULN, or
 - ALT $> 8 \times ULN$ if baseline ALT $> 2 \times ULN$.
- Pregnancy of a female subject entered in a study as well as pregnancy occurring in a female partner of a male subject entered in a study with IMP/NIMP.

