AESI and other AE groupings	Incidence of each type of AESI and other AE groupings will be tabulated by treatment group. For each type of AESI, the following analysis will be generated. • A summary of the number (%) of patients with - Any TEAE. - Any SAE (regardless of treatment-emergent status). - Any treatment-emergent SAE. - Any AE leading to death. - Any TEAE leading to death. - Any TEAE leading permanent treatment discontinuation. - Any TEAE related to IMP reported by Investigator. - Number of patients with the TEAE per 100 patient-years. - Any TEAE by maximum intensity, corrective treatment, and final outcome. • Kaplan-Meier (K-M) estimates of probability of having at least one TEAE at specific time points, and K-M curve to depict the course of event onset over time. The method to identify AESIs and other AE groupings will be specified in the SAP.
Death	 The following deaths summaries will be generated: Number (%) of patients who died by study period (TEAE, on-study) summarized on the safety population by treatment received. Death in nonrandomized patients or randomized and not treated patients. Treatment-emergent AE leading to death (death as an outcome on the AE eCRF page as reported by the Investigator) by primary SOC, HLGT, HLT, and PT showing number (%) of patients sorted by internationally agreed order of SOC and alphabetic order of HLGT, HLT, and PT.

28-Oct-2023 Version number: 1

Endpoint	Statistical Analysis Methods
Laboratory parameters	Results and change from baseline for the parameters will be summarized by treatment group for baseline and each post baseline time point, endpoint, minimum and maximum value. Summary statistics will include number of patients, mean, standard deviation, median, Q1, Q3, minimum, and maximum.
	The following definitions will be applied to laboratory parameters.
	 The potentially clinically significant abnormality (PCSA) values are defined as abnormal values considered medically important by the Sponsor according to predefined criteria/thresholds based on literature review and defined by the Sponsor for clinical laboratory tests. PCSA criteria will determine which patients had at least 1 PCSA during the on-treatment period, taking into account all evaluations performed during the on-treatment period, including unscheduled or repeated evaluations. The number of all such patients will be the numerator for the
	on-treatment PCSA percentage.

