2.1.4.1 Adverse events variables

Adverse event observation period

- Pretreatment adverse events are adverse events that developed or worsened or became serious during the screening epoch
- Treatment-emergent adverse events are adverse events that developed or worsened or became serious during the treatment-emergent adverse event period
- Posttreatment adverse events are adverse events that developed or worsened or became serious during the posttreatment epoch.

All adverse events (including serious adverse events and adverse events with pre-specified monitoring/of special interests) will be coded to a lower-level term (LLT), preferred term (PT), high-level term (HLT), high-level group term (HLGT), and associated primary system organ class (SOC) using the version of Medical Dictionary for Regulatory Activities (MedDRA) currently in effect at Sanofi at the time of database lock.

The occurrence of adverse events (including serious adverse events and adverse events with prespecified monitoring) will be recorded from the time of signed informed consent until the end of the study.

Cardiovascular assessment

All events submitted for cardiovascular adjudication will be listed and summarized, including the final classification results. A swimmer plot including all events classified as cardiovascular, including cardiovascular death, will also be provided.

Furthermore, events classified as cardiovascular will be evaluated according to the following composite endpoints:

- **Major Cardiovascular Adverse Events (MACE):** cardiovascular death, non-fatal myocardial infarction, or non-fatal stroke
- MACE + hospitalization for unstable angina
- Cardiovascular death: death resulting from myocardial infarction, stroke, pulmonary embolism, heart failure, procedure-related death or other cardiovascular cause.
- Hospitalization: for unstable angina, for atrial fibrillation/flutter, for other symptomatic arrhythmias, for transient ischemic attack.
- Other cardio/cerebrovascular events: non-fatal heart failure, peripheral arterial event, pulmonary embolism, non-acute coronary syndrome/myocardial ischemia, others.

Adverse events of special interest (AESI) and other selected AE groupings will be searched based on the criteria in [Table 2](#).

Table 2 - Criteria for adverse events of special interest and other selected AE groupings

AE Grouping	Criteria
AESI	

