Anaphylactic reaction	Anaphylactic reaction algorithmic approach (Introductory Guide for Standardised MedDRA Queries (SMQs) Version 18.1): includes anaphylactic reaction narrow SMQ (20000021) terms and programmatic identification of cases based on occurrence of at least two preferred terms meeting the algorithm criteria occurring within 24 hours of each other. The latter cases identified using the algorithm will undergo blinded medical review taking into account the timing of events relative to each other and to IMP administration for final determination of an anaphylactic reaction or not.
Hypersensitivity (medically reviewed)	SMQ hypersensitivity (20000214) narrow search and [AE corrective treatment/therapy='Y' or Action taken with IMP='Drug withdrawn' or Action taken with IMP='Drug interrupted'] followed by blinded medical review (documented process) for selection of relevant systemic hypersensitivity events
Severe injection site reactions that last longer than 24 hours	HLT = 'Injection site reactions' and with severe status and (AE end date/time - AE start date/time) ≥eg, 24 hours or ongoing
Serious infection	Primary SOC = 'Infections and infestations' and with serious status
Parasitic infection	The Infection Type 'Parasitic' was checked on eCRF page "Infection Event Form"

AE Grouping	Criteria
Infection requires parenteral (intravenous, intramuscular, subcutaneous) antimicrobial therapy	"Have any parenteral treatment (IV, Intramuscular, SC) been given for this event?" was answered Yes on eCRF page "Infection Event Form"
Infection requires oral antimicrobial therapy for longer than 2 weeks	"Did this event require Prolonged Medication (greater than 14 Days)?" was answered Yes on eCRF page "Infection Event Form"
Opportunistic infection	The Infection Type 'Opportunistic' was checked on eCRF page "Infection Event Form"
Pregnancy of a female patient entered in a study as well as pregnancy occurring in a female partner of a male patient entered in a study with IMP/NIMP	"Pregnancy" or "Partner Pregnancy" checked on the Pregnancy eCRF page as reported by the investigator
Symptomatic overdose with IMP	Symptomatic Overdose is answered Yes, with Overdose of IMP answered Yes on AE eCRF.
Symptomatic overdose with NIMP	Symptomatic Overdose is answered Yes, with Overdose of NIMP answered Yes on AE eCRF.

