Appendix I List of opportunistic infections

- Aspergillosis
- Blastomyces dermatitidis (endemic in the south-eastern and south-central states US, along Mississippi and Ohio Rivers)
- Candidiasis – Note that all cases should be collected as AEs. only systemic or extensive mucosal or cutaneous candidiasis is considered opportunistic infections
- Coccidioides immitis (endemic south-western US and Central and South America)
- Cryptococcus
- Cytomegalovirus
- Herpes Simplex (disseminated)
- Herpes Zoster (disseminated; ophthalmic; involvement of 2 or more dermatomes)
- Histoplasmosis (pulmonary or disseminated; most common tropical areas Tennessee-Ohio-Mississippi river basins)
- Listeriosis
- Mycobacterium avium
- Nontuberculosis mycobacteria
- Pneumocystis pneumonia (PCP)

This list is indicative and not exhaustive

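### The SAP counts the opportunistic-infection AESI only from an eCRF tick, with no coded-term check against the protocol's Appendix 16; separately, the SAP's copy of that list omits tuberculosis

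*Protocol*

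**What the plan says.** **Definition.** Protocol 8.3.1 lists five criteria, any one of which makes an infection an AESI. One of them is "Is an opportunistic infection (see Appendix 16, Section 10.16"). Appendix 16 (section 10.16) gives 14 entries, including "Mycobacterium tuberculosis", cytomegalovirus, and zoster that is disseminated, ophthalmic or involves at least two dermatomes. It closes with "This list is indicative and not exhaustive". Protocol 7.1.1 refers to the same concept and takes TB as its example: "Any opportunistic infection, such as TB or other infections whose nature or course may suggest an immunocompromised status".

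**Identification.** Protocol 9.4.2 (Table 10) hands the method over: "The method to identify AESIs and other AE groupings will be specified in the SAP". SAP 2.1.4.1 takes it up: "Adverse events of special interest (AESI) and other selected AE groupings will be searched based on the criteria in" Table 2. For opportunistic infection, Table 2 has a single criterion: "The Infection Type 'Opportunistic' was checked on eCRF page", the page being the Infection Event Form.

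**The SAP's own list.** SAP Appendix I has 13 entries. It goes from listeriosis straight to "Mycobacterium avium", with no tuberculosis entry. SAP 1.6, on modifications made in the SAP, says not applicable.

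**Use.** SAP 2.4.5.1 plans risk differences and hazard ratios with 95% confidence intervals for the AESI table. SAP 2.4.5 calls the safety analysis essentially descriptive.

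**The concern.** The protocol defines this event by what the infection is; the SAP counts it by what the investigator marked on a form. The two agree only as far as the box is ticked for every infection that Appendix 16 covers. Nothing in the SAP compares the coded terms with the list, so a discrepancy would go unseen.

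Opportunistic infection matters for an immunomodulating antibody, and the protocol requires the sponsor to be told of it within 24 hours. If few events occur, one missed case can visibly move the row's risk difference or hazard ratio.

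The shortened list adds a second difficulty. Anyone who later treats SAP Appendix I as the reference, for example when writing a term list or answering a query, would be working from a list that differs from the protocol's by one named organism, and the change is not declared.

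**Working it through.** The plan states no figure on this point, so the check compares the texts and traces the rule.

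**1. Which text governs the count.** Protocol Table 10 defers to the SAP, and SAP 2.1.4.1 defers to Table 2. The Table 2 criterion therefore decides what enters the row.

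**2. How Table 2 treats other groupings.**
- Hypersensitivity: coded terms plus treatment or action-taken conditions, then blinded medical review.
- Anaphylaxis: narrow SMQ terms, plus algorithm-identified cases that get blinded medical review.
- Symptomatic eosinophilia: coded terms, then blinded medical review.
- Keratitis: a preferred-term list.
- Serious infection: system organ class plus seriousness.
- Parasitic infection: a tick, partly backed by a separate coded grouping for helminthic infections.
- Opportunistic infection: a tick, with no coded counterpart.

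A coded check would therefore not be a new kind of method in this table.

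**3. Where an Appendix 16 infection goes under the current rule.**

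| Event | Opportunistic row | Another infection AESI row |
|---|---|---|
| Ticked, any organism including TB | Yes | As applicable |
| Unticked, serious | No | Yes, serious infection |
| Unticked, non-serious, parenteral treatment | No | Yes, parenteral row |
| Unticked, non-serious, more than 14 days of medication | No | Yes, prolonged-therapy row |
| Unticked, none of these | No | No |

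Only the last line can drop out of the AESI output altogether. A two-dermatome zoster treated orally for 14 days or less, and not serious, would fit it. Some such cases may still surface elsewhere: the keratitis term list, for instance, includes herpes ophthalmic. All of these events remain in the general treatment-emergent AE tables and listing. SAP 2.4.5.1 also summarises investigator-reported AESIs separately, but that again depends on the investigator and is not an independent check.

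**4. The two lists, entry by entry.** Protocol 14, SAP 13; 14 - 13 = 1. The one missing organism is Mycobacterium tuberculosis. The candidiasis entry is reworded, but what counts as opportunistic is unchanged.

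**5. Whether the list difference reaches the count.** Table 2 does not cite Appendix I. In the text supplied, Appendix I appears only in the table of contents, the list of appendices and on its own page. Both lists are described as open-ended. The omission therefore removes no event under the current rule.

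**6. Size.** The documents give neither infection rates nor tick completeness, so no under-count can be calculated. Purely as illustration, assume 6 versus 2 true cases with the planned 462 patients per arm. The risk difference is (6 - 2)/462 = 0.87 percentage points. If the tick captured 50% in both arms, the row would show 3 versus 1, or 2/462 = 0.43 points. At 90% it would show 5.4 versus 1.8 in expectation, or 3.6/462 = 0.78 points. The ratio of cases stays at 3 to 1 throughout. The case counts and both capture rates are invented for the example.

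**The case against.** The case for leaving Table 2 alone is reasonable. Investigators work from the protocol, which names TB twice, and must report AESIs within 24 hours, so TB is among the infections least likely to go unticked. Protocol E19 also excludes active, untreated latent and incompletely treated tuberculosis, unless a specialist documents adequate treatment. Form-based identification is used elsewhere in Table 2, for pregnancy, overdose and ALT elevation. Opportunistic status depends on dissemination, extent or number of dermatomes, which a preferred term may not carry. The form's completion instructions are not in the documents, and nothing shows that the box is under-ticked. Safety analysis is descriptive, so no formal test depends on this row.

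Most of that stands, and it keeps the point small. It does not remove the gap: if a box is missed, the SAP provides no way to find the case. The limits of preferred terms are a reason for medical review of term-only cases, not for omitting the term search.

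The objection also disposes of two stronger readings. A reader might infer that dropping tuberculosis from SAP Appendix I makes TB cases disappear from the table. The documents do not support this, because Table 2 does not use Appendix I and a ticked TB case is counted. A reader might also infer that unticked cases vanish from the AESI output. That is true only for those that are also non-serious, without parenteral treatment and without prolonged medication, a description that an unticked TB case would usually not meet.

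**Conclusion.** The point holds as a minor one. Under SAP Table 2, an infection that protocol Appendix 16 covers but the investigator does not tick is absent from the opportunistic-infection row, and no coded-term search or medical review would find it. Absence from all AESI rows needs the further conditions set out in the trace.

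The missing tuberculosis entry in SAP Appendix I is a separate inconsistency with no effect on any count as the plan stands.

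The size of any under-count is unknown and cannot be derived from the documents. The illustrative figures show only the direction: incomplete ticking that is equal in both arms would shrink a risk difference while leaving the expected ratio about the same. They are not evidence that events are being lost, and a claim that the safety conclusions are biased would go beyond what the documents show.

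**What to change.** 1. In SAP Table 2, define the opportunistic-infection row as: the infection type 'Opportunistic' ticked on the Infection Event Form, or a preferred term matching an infection in protocol Appendix 16. Cases found by term only go to blinded medical review, which applies the list's qualifiers (disseminated, extensive, two or more dermatomes).
2. Fix the term list and complete the review before database lock. Because the interim lock becomes the primary analysis if efficacy is shown then (SAP section 4), this means before the interim lock.
3. Restore Mycobacterium tuberculosis to SAP Appendix I so that it matches protocol Appendix 16, and cite the list from Table 2.

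The cost is a short term list, some SAP wording and a little medical-review time. A few more events may be counted in either arm. No treatment rule and no efficacy analysis changes.
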